#### 13. Seizures

Medical concept of seizures. Only narrow terms from SMQ 'Convulsions' selected plus selected PTs of possible seizure events from HLT 'Disturbances in consciousness NEC' under SOC 'Nervous systems disorders' and HLT 'Confusion and disorientation' under SOC 'Psychiatric disorders'.

SMQ: 'Convulsions' SMQ Code: 20000079 Category: A Scope: Narrow	
Preferred Term	PT Code
1p36 deletion syndrome	10082398
2-Hydroxyglutaric aciduria	10078971
Acquired epileptic aphasia	10052075
Acute encephalitis with refractory, repetitive partial seizures	10076948
Alcoholic seizure	10056347
Aspartate-glutamate-transporter deficiency	10079140
Atonic seizures	10003628
Atypical benign partial epilepsy	10056699
Automatism epileptic	10003831
Autonomic seizure	10049612
Baltic myoclonic epilepsy	10054895
Benign familial neonatal convulsions	10067866
Benign rolandic epilepsy	10070530
Biotinidase deficiency	10071434
Change in seizure presentation	10075606
Clonic convulsion	10053398
Convulsion in childhood	10052391
Convulsions local	10010920
Convulsive threshold lowered	10010927
CSWS syndrome	10078827
Deja vu	10012177
Double cortex syndrome	10073490
Dreamy state	10013634
Drug withdrawal convulsions	10013752
Early infantile epileptic encephalopathy with burst-suppression	10071545

Eclampsia	10014129
Epilepsy	10015037
Epilepsy surgery	10079824
Epilepsy with myoclonic-atonic seizures	10081179
Epileptic aura	10015049
Epileptic psychosis	10059232
Febrile convulsion	10016284
Febrile infection-related epilepsy syndrome	10079438
Focal dyscognitive seizures	10079424
Frontal lobe epilepsy	10049424
Generalised non-convulsive epilepsy	10018090
Generalised tonic-clonic seizure	10018100
Glucose transporter type 1 deficiency syndrome	10078727
Grey matter heterotopia	10082084
Hemimegalencephaly	10078100
Hyperglycaemic seizure	10071394
Hypocalcaemic seizure	10072456
Hypoglycaemic seizure	10048803
Hyponatraemic seizure	10073183
Idiopathic generalised epilepsy	10071081
Infantile spasms	10021750
Juvenile myoclonic epilepsy	10071082
Lafora's myoclonic epilepsy	10054030
Lennox-Gastaut syndrome	10048816
Migraine-triggered seizure	10076676
Molybdenum cofactor deficiency	10069687
Multiple subpial transection	10079825
Myoclonic epilepsy	10054859
Myoclonic epilepsy and ragged-red fibres	10069825

Partial seizures         10061334           Partial seizures with secondary generalisation         10056209           Petit mal epilepsy         10034759           Polymicrogyria         10073489           Post stroke epilepsy         10076982           Post stroke seizure         10076981           Postictal headache         10052470           Postictal paralysis         10052469           Postictal psychosis         10070669           Postictal state         10048727           Post-traumatic epilepsy         10036312           Schizencephaly         10073487           Seizure         10039906           Seizure anoxic         10039907           Seizure cluster         10071048           Severe myoclonic epilepsy of infancy         10071048           Severe myoclonic epilepsy of infancy         10040703           Status epilepticus         10040703           Status epilepticus         10040703           Status epilepticus         10043209           Tonic clonic movements         10051171           Tonic convulsion         10043209           Tonic convulsion         10075125           Topectomy         10073488           Transient epileptic amnesia	Neonatal epileptic seizure	10082068
Partial seizures with secondary generalisation         10056209           Petit mal epilepsy         10034759           Polymicrogyria         10073489           Post stroke epilepsy         10076982           Post stroke seizure         10076981           Postictal headache         10052470           Postictal paralysis         10052469           Postictal psychosis         10070669           Post-traumatic epilepsy         10036312           Schizencephaly         10073487           Seizure         10039906           Seizure anoxic         10039907           Seizure cluster         10071350           Seizure like phenomena         10071048           Severe myoclonic epilepsy of infancy         10073677           Simple partial seizures         10040703           Status epilepticus         10040703           Status epilepticus         10043209           Tonic clonic movements         10051171           Tonic convulsion         10043994           Tonic posturing         10073488           Transient epileptic amnesia         10081728	Neonatal seizure	10082067
Petit mal epilepsy         10034759           Polymicrogyria         10073489           Post stroke epilepsy         10076982           Post stroke seizure         10076981           Postictal headache         10052470           Postictal paralysis         10052469           Postictal psychosis         10070669           Postictal state         10048727           Post-traumatic epilepsy         10036312           Schizencephaly         10073487           Seizure         10039906           Seizure anoxic         10039907           Seizure cluster         10071350           Seizure like phenomena         10071048           Severe myoclonic epilepsy of infancy         10073677           Simple partial seizures         10040703           Status epilepticus         10040703           Status epilepticus         10043209           Temporal lobe epilepsy         10063894           Temporal lobe epilepsy         10043209           Tonic clonic movements         10051171           Tonic posturing         10075125           Topectomy         10073488           Transient epileptic amnesia         10081728	Partial seizures	10061334
Polymicrogyria         10073489           Post stroke epilepsy         10076982           Post stroke seizure         10076981           Postictal headache         10052470           Postictal paralysis         10052469           Postictal psychosis         10070669           Post-traumatic epilepsy         10036312           Schizencephaly         10073487           Seizure         10039906           Seizure anoxic         10039907           Seizure cluster         10071350           Seizure like phenomena         10071048           Severe myoclonic epilepsy of infancy         10073677           Simple partial seizures         10040703           Status epilepticus         10040703           Status epilepticus         10040703           Temporal lobe epilepsy         10063894           Temporal lobe epilepsy         10043209           Tonic clonic movements         10051171           Tonic posturing         10075125           Topectomy         10073488           Transient epileptic amnesia         10081728	Partial seizures with secondary generalisation	10056209
Post stroke epilepsy         10076982           Post stroke seizure         10076981           Post ictal headache         10052470           Postictal paralysis         10052469           Postictal psychosis         10070669           Postictal state         10048727           Post-traumatic epilepsy         10036312           Schizencephaly         10073487           Seizure         10039906           Seizure anoxic         10039907           Seizure cluster         10071350           Seizure like phenomena         10071048           Severe myoclonic epilepsy of infancy         10073677           Simple partial seizures         10040703           Status epilepticus         10040703           Status epilepticus         10043209           Tonic clonic movements         10051171           Tonic clonic movements         10051171           Tonic convulsion         10043994           Tonic posturing         10073488           Transient epileptic amnesia         10081728	Petit mal epilepsy	10034759
Post stroke seizure         10076981           Postictal headache         10052470           Postictal paralysis         10052469           Postictal psychosis         10070669           Postictal state         10048727           Post-traumatic epilepsy         10036312           Schizencephaly         10073487           Seizure         10039906           Seizure anoxic         10039907           Seizure cluster         10071048           Severe myoclonic epilepsy of infancy         10073677           Simple partial seizures         10040703           Status epilepticus         10040703           Status epilepticus         10043994           Temporal lobe epilepsy         10043209           Tonic clonic movements         10051171           Tonic convulsion         10043994           Tonic posturing         10073488           Transient epileptic amnesia         10081728	Polymicrogyria	10073489
Postictal headache         10052470           Postictal paralysis         10052469           Postictal psychosis         10070669           Postictal state         10048727           Post-traumatic epilepsy         10036312           Schizencephaly         10073487           Seizure         10039906           Seizure anoxic         10039907           Seizure cluster         10071350           Seizure like phenomena         10071048           Severe myoclonic epilepsy of infancy         10073677           Simple partial seizures         10040703           Status epilepticus         10040703           Status epilepticus         10043994           Temporal lobe epilepsy         10043994           Tonic clonic movements         10043994           Tonic posturing         10075125           Topectomy         10073488           Transient epileptic amnesia         10081728	Post stroke epilepsy	10076982
Postictal paralysis         10052469           Postictal psychosis         10070669           Postictal state         10048727           Post-traumatic epilepsy         10036312           Schizencephaly         10073487           Seizure         10039906           Seizure anoxic         10039907           Seizure cluster         10071350           Seizure like phenomena         10071048           Severe myoclonic epilepsy of infancy         10073677           Simple partial seizures         10040703           Status epilepticus         10041962           Sudden unexplained death in epilepsy         10063894           Temporal lobe epilepsy         10043209           Tonic clonic movements         10051171           Tonic convulsion         10043994           Tonic posturing         10075125           Topectomy         10073488           Transient epileptic amnesia         10081728	Post stroke seizure	10076981
Postictal psychosis         10070669           Postictal state         10048727           Post-traumatic epilepsy         10036312           Schizencephaly         10073487           Seizure         10039906           Seizure anoxic         10039907           Seizure cluster         10071350           Seizure like phenomena         10071048           Severe myoclonic epilepsy of infancy         10073677           Simple partial seizures         10040703           Status epilepticus         10041962           Sudden unexplained death in epilepsy         10063894           Temporal lobe epilepsy         10051171           Tonic clonic movements         10051171           Tonic convulsion         10043994           Tonic posturing         10075125           Topectomy         10073488           Transient epileptic amnesia         10081728	Postictal headache	10052470
Postictal state         10048727           Post-traumatic epilepsy         10036312           Schizencephaly         10073487           Seizure         10039906           Seizure anoxic         10039907           Seizure cluster         10071350           Seizure like phenomena         10071048           Severe myoclonic epilepsy of infancy         10073677           Simple partial seizures         10040703           Status epilepticus         10041962           Sudden unexplained death in epilepsy         10063894           Temporal lobe epilepsy         10051171           Tonic clonic movements         10051171           Tonic convulsion         10043994           Tonic posturing         10075125           Topectomy         10073488           Transient epileptic amnesia         10081728	Postictal paralysis	10052469
Post-traumatic epilepsy         10036312           Schizencephaly         10073487           Seizure         10039906           Seizure anoxic         10039907           Seizure cluster         10071350           Seizure like phenomena         10071048           Severe myoclonic epilepsy of infancy         10073677           Simple partial seizures         10040703           Status epilepticus         10041962           Sudden unexplained death in epilepsy         10063894           Temporal lobe epilepsy         10043209           Tonic clonic movements         10051171           Tonic convulsion         10043994           Tonic posturing         10075125           Topectomy         10073488           Transient epileptic amnesia         10081728	Postictal psychosis	10070669
Schizencephaly       10073487         Seizure       10039906         Seizure anoxic       10039907         Seizure cluster       10071350         Seizure like phenomena       10071048         Severe myoclonic epilepsy of infancy       10073677         Simple partial seizures       10040703         Status epilepticus       10041962         Sudden unexplained death in epilepsy       10063894         Temporal lobe epilepsy       10043209         Tonic clonic movements       10051171         Tonic convulsion       10043994         Tonic posturing       10075125         Topectomy       10073488         Transient epileptic amnesia       10081728	Postictal state	10048727
Seizure       10039906         Seizure anoxic       10039907         Seizure cluster       10071350         Seizure like phenomena       10071048         Severe myoclonic epilepsy of infancy       10073677         Simple partial seizures       10040703         Status epilepticus       10041962         Sudden unexplained death in epilepsy       10063894         Temporal lobe epilepsy       10043209         Tonic clonic movements       10051171         Tonic convulsion       10043994         Tonic posturing       10075125         Topectomy       10073488         Transient epileptic amnesia       10081728	Post-traumatic epilepsy	10036312
Seizure anoxic       10039907         Seizure cluster       10071350         Seizure like phenomena       10071048         Severe myoclonic epilepsy of infancy       10073677         Simple partial seizures       10040703         Status epilepticus       10041962         Sudden unexplained death in epilepsy       10063894         Temporal lobe epilepsy       10043209         Tonic clonic movements       10051171         Tonic convulsion       10043994         Tonic posturing       10075125         Topectomy       10073488         Transient epileptic amnesia       10081728	Schizencephaly	10073487
Seizure cluster       10071350         Seizure like phenomena       10071048         Severe myoclonic epilepsy of infancy       10073677         Simple partial seizures       10040703         Status epilepticus       10041962         Sudden unexplained death in epilepsy       10063894         Temporal lobe epilepsy       10043209         Tonic clonic movements       10051171         Tonic convulsion       10043994         Tonic posturing       10075125         Topectomy       10073488         Transient epileptic amnesia       10081728	Seizure	10039906
Seizure like phenomena 10071048 Severe myoclonic epilepsy of infancy 10073677 Simple partial seizures 10040703 Status epilepticus 10041962 Sudden unexplained death in epilepsy 10063894 Temporal lobe epilepsy 10043209 Tonic clonic movements 10051171 Tonic convulsion 10043994 Tonic posturing 10075125 Topectomy 10081728	Seizure anoxic	10039907
Severe myoclonic epilepsy of infancy  Simple partial seizures  10040703  Status epilepticus  10041962  Sudden unexplained death in epilepsy  Temporal lobe epilepsy  Tonic clonic movements  10051171  Tonic convulsion  10043294  Tonic posturing  10075125  Topectomy  Transient epileptic amnesia	Seizure cluster	10071350
Simple partial seizures 10040703 Status epilepticus 10041962 Sudden unexplained death in epilepsy 10063894 Temporal lobe epilepsy 10043209 Tonic clonic movements 10051171 Tonic convulsion 10043994 Tonic posturing 10075125 Topectomy 10073488 Transient epileptic amnesia 10081728	Seizure like phenomena	10071048
Status epilepticus 10041962 Sudden unexplained death in epilepsy 10063894 Temporal lobe epilepsy 10043209 Tonic clonic movements 10051171 Tonic convulsion 10043994 Tonic posturing 10075125 Topectomy 10073488 Transient epileptic amnesia 10081728	Severe myoclonic epilepsy of infancy	10073677
Sudden unexplained death in epilepsy Temporal lobe epilepsy Tonic clonic movements Tonic convulsion Tonic posturing Topectomy Topectomy Transient epileptic amnesia  10063894 10043209 10051171 10043294 10075125 10073488	Simple partial seizures	10040703
Temporal lobe epilepsy  Tonic clonic movements  10051171  Tonic convulsion  10043209  Tonic convulsion  10043994  Tonic posturing  10075125  Topectomy  10073488  Transient epileptic amnesia  10081728	Status epilepticus	10041962
Tonic clonic movements       10051171         Tonic convulsion       10043994         Tonic posturing       10075125         Topectomy       10073488         Transient epileptic amnesia       10081728	Sudden unexplained death in epilepsy	10063894
Tonic convulsion       10043994         Tonic posturing       10075125         Topectomy       10073488         Transient epileptic amnesia       10081728	Temporal lobe epilepsy	10043209
Tonic posturing 10075125 Topectomy 10073488 Transient epileptic amnesia 10081728	Tonic clonic movements	10051171
Topectomy 10073488  Transient epileptic amnesia 10081728	Tonic convulsion	10043994
Transient epileptic amnesia 10081728	Tonic posturing	10075125
· · ·	Topectomy	10073488
Tuberous sclerosis complex 10080584	Transient epileptic amnesia	10081728
	Tuberous sclerosis complex	10080584

Uncinate fits	10045476
Additional selected preferred terms from HLT 'Disturbances in consciousness NEC' under SOC 'Nervous systems disorders' and HLT 'Confusion and disorientation' under SOC 'Psychiatric disorders'.	
Preferred Term	PT Code
Confusional state	10010305
Loss of consciousness	10024855
Syncope	10042772
Sopor	10058709
Stupor	10042264
Altered state of consciousness	10001854
Depressed level of consciousness	10012373
Consciousness fluctuating	10050093

## 14. Weight Gain

Medical concept of weight gain. Selected PTs from HLT 'General nutritional disorders NEC', under SOC 'Metabolism and nutrition disorders', and HLT 'Physical examination procedures and organ system status', under SOC 'Investigations' and HLT 'General signs and symptoms NEC', under SOC 'General disorders and administration site conditions'.

Preferred Term	PT Code
Abdominal fat apron	10077983
Overweight	10033307
Abnormal weight gain	10000188
Central obesity	10065941
Obesity	10029883
Weight abnormal	10056814
Weight increased	10047899
Waist circumference increased	10064863
Body mass index abnormal	10074506
Body mass index increased	10005897
Fat tissue increased	10016251

## 15. Rhabdomyolysis

Medical concept of rhabdomyolysis. Only narrow terms only for SMQ 'Rhabdomyolysis/myopathy' plus 2 additional preferred terms selected from HGLT 'muscle disorders' under SOC 'Musculoskeletal and connective tissue disorders'.

SMQ: 'Rhabdomyolysis/myopathy' SMQ Code: 20000002 Category: A Scope: Narrow	
Preferred Term	PT Code
Muscle necrosis	10028320
Myoglobin blood increased	10028625
Myoglobin blood present	10059888
Myoglobin urine present	10028631
Myoglobinaemia	10058735
Myoglobinuria	10028629
Myopathy	10028641
Myopathy toxic	10028648
Necrotising myositis	10074769
Rhabdomyolysis	10039020
Thyrotoxic myopathy	10081524
Additional selected preferred terms from HLGT 'muscle disorders' under SOC 'Musculoskeletal and connective tissue disorders'	
Preferred Term	PT Code
Myalgia	10028411
Myositis	10028653

#### 16. Pancreatitis

Medical concept of acute pancreatitis. Only narrow terms of SMQ 'Acute pancreatitis' selected. Algorithmic approach for this SMQ not used due to complexity in applying and poor specificity of remaining categories. Category A selected as PTs because more specific for concept (only narrow terms).

SMQ: 'Acute pancreatitis' SMQ Code: 20000022 Category: A Scope: Narrow	
Preferred Term	PT Code
Cullen's sign	10059029
Grey Turner's sign	10075426
Haemorrhagic necrotic pancreatitis	10076058
Hereditary pancreatitis	10056976
Ischaemic pancreatitis	10066127
Oedematous pancreatitis	10052400
Pancreatic abscess	10048984
Pancreatic cyst drainage	10082531
Pancreatic haemorrhage	10033625
Pancreatic necrosis	10058096
Pancreatic phlegmon	10056975
Pancreatic pseudoaneurysm	10081762
Pancreatic pseudocyst	10033635
Pancreatic pseudocyst drainage	10033636
Pancreatitis	10033645
Pancreatitis acute	10033647
Pancreatitis haemorrhagic	10033650
Pancreatitis necrotising	10033654
Pancreatitis relapsing	10033657
Pancreatorenal syndrome	10056277

## 17. Impact on Creatinine

Medical concept of worsening renal function/renal failure in the context of impact on creatinine. Only narrow terms from SMQ 'Acute renal failure' plus all PTs from HLT 'Renal failure and impairment', under SOC 'Renal and urinary disorders'. Numerous duplicated preferred terms e.g. renal failure.

SMQ: 'Acute renal failure' SMQ Code: 20000003 Category: A Scope: Narrow	
Preferred Term	PT Code
Acute kidney injury	10069339
Acute phosphate nephropathy	10069688
Anuria	10002847
Azotaemia	10003885
Continuous haemodiafiltration	10066338
Dialysis	10061105
Foetal renal impairment	10078987
Haemodialysis	10018875
Haemofiltration	10053090
Neonatal anuria	10049778
Nephropathy toxic	10029155
Oliguria	10030302
Peritoneal dialysis	10034660
Prerenal failure	10072370
Renal failure	10038435
Renal failure neonatal	10038447
Renal impairment	10062237
Renal impairment neonatal	10049776
Subactute kidney injury	10081980
Plus, all PTs from HLT 'Renal failure and impairment' under SOC 'Renal and urinary disorders'	
Preferred Term	PT Code
Acute Kidney injury	10069339
Anuria	10002847
Atypical haemolytic uraemic syndrome	10079840

Cardiorenal syndrome	10068230
Chronic kidney disease	10064848
Crush syndrome	10050702
Diabetic end stage renal disease	10012660
End stage renal disease	10077512
Foetal renal impairment	10078987
Haemolytic uraemic syndrome	10018932
Hepatorenal failure	10019845
Hepatorenal syndrome	10019846
Nail-patella syndrome	10063431
Neonatal anuria	10049778
Oliguria	10030302
Pancreatorenal syndrome	10056277
Postoperative renal failure	10056675
Postrenal failure	10059345
Prerenal failure	10072370
Propofol infusion syndrome	10063181
Renal failure	10038435
Renal failure neonatal	10038447
Renal impairment	10062237
Renal impairment neonatal	10049776
Renal injury	10061481
Scleroderma renal crisis	10062553
Traumatic anuria	10044501
	·

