DTG & RPV: Increased rates of virologic failure/ Observed Resistance	
Virologically suppressed subjects switching from oral CAB + RPV to DTG + RPV may experience virologic failure/breakthrough and development of resistance.
 
DTG: Week 96 and Week 144 analyses for the Phase III/IIIb clinical studies supported the efficacy findings from earlier analyses, and demonstrated robust maintenance of viral suppression with no finding of HIV-1 resistance in treatment-naïve subjects.
 
RPV: In Phase III clinical trials (pooled Week 96 analyses), 3.2% of patients in the RPV arm experienced virologic failure between Week 48 and Week 96 (2.3 % on EFV).
	Subjects will have HIV-1 RNA measured at each study visit. Management of subjects experiencing increase in viral load is described in Section 7.1.5.
DTG: Theoretical serious drug interaction with dofetilide and pilsicainide	Co-administration of DTG may increase dofetilide/pilsicainide plasma concentration via inhibition of organic cation transporter (OCT-2), resulting in potentially life-threatening toxicity.	The co-administration of DTG with dofetilide or pilsicainide is prohibited in the study (Section 6.11.2.4).
DTG: Renal function	Mild elevations of creatinine have been observed with DTG which are related to a likely benign effect on creatinine secretion with blockade of OCT-2. DTG has been shown to have no significant effect on glomerular filtration rate (GFR) or effective renal plasma flow.	Specific/detailed toxicity management guidance is provided for subjects who develop a decline in renal function (Section 8.7.7).
DTG: Creatine Phosphokinase (CPK) elevations	Asymptomatic CPK elevations mainly in association with exercise have been reported with DTG therapy.	Specific detailed toxicity management guidance is provided for subjects who develop Grade 3 to 4 CPK elevations (Section 8.7.5).

Potential Risk of Clinical Significance	Data/Rationale for Risk	Mitigation Strategy ^a
Commercial Juluca [DTG and RPV] Refer to IBs for additional information		

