8.7.7. Decline in Renal Function

Participants who experience an increase in serum creatinine from Baseline of 45 micromoles/liter ($\mu\text{Mol/L}$) (or 0.5 milligrams/deciliter [mg/dL]) should return for a confirmatory assessment within 2 to 4 weeks. A urinalysis and urine albumin/creatinine and urine total protein/albumin ratios should also be done at this confirmatory visit. If the creatinine increase is confirmed, the investigator should contact the study medical monitor to discuss additional follow-up and medical management.

Participants who have a decline in the estimated GFR (using the CKD-EPI method) of $>50\%$ from Baseline must return for a confirmatory assessment as soon as possible [Levey, 2009]. A urinalysis and urine albumin/creatinine and urine protein/creatinine ratios should also be done at this confirmatory visit. If the estimated GFR has declined by $>50\%$ (confirmed), then study drug should be withheld and the investigator should contact the study medical monitor to discuss the rationale for restarting study drugs (if appropriate). Consideration for confounding factors (e.g., background therapy, other medications, dehydration, concurrent conditions) should be taken into account, and a nephrology consult may be obtained.

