Impact on Creatinine	CAB+RPV	Regulatory Interest, Therapeutic Area, More prevalent in HIV population
Safety in Pregnancy	CAB	Regulatory Interest, Class

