# 12.10. Appendix 10: Identification of Adverse Events of Special Interest

The adverse events of special interest are identified based on MedDRA coded values and/or AE data available in the study database. The system organ classes (SOCs), preferred terms (PTs) or codes, Standardised MedDRA Queries (SMQs), High Level Group Terms (HLGTs), and High Level Terms (HLTs) below are from MedDRA 22.0. In case there is a change to the version of MedDRA at time of reporting, the coded values based on the MedDRA version at the time of reporting will be used. The additional events may also be added based on the blinded review of AE data collected on study prior to the database freeze.

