3.37.	Safety	207966/primar y_02/T3.70	Summary of Prolongation of the Corrected QT Interval of the ECG in Supra Therapeutic Doses Adverse Events of Special Interest by System Organ Class and Preferred Term (Number of Subjects and Occurrences)		M12, M26, EOS			
3.38.	Safety	207966/primar y_02/T3.73	Summary of Bipolar Disorder Adverse Events of Special Interest by System Organ Class and Preferred Term (Number of Subjects and Occurrences)		M12, M26, EOS			
3.39.	Safety	207966/primar y_02/T3.74	Summary of Psychosis Adverse Events of Special Interest by System Organ Class and Preferred Term (Number of Subjects and Occurrences)		M12, M26, EOS			
3.40.	Safety	207966/primar y_02/T3.75	Summary of Mood Disorder Adverse Events of Special Interest by System Organ Class and Preferred Term (Number of Subjects and Occurrences)		M12, M26, EOS			

Safety	Safety: Tables							
No.	Population	IDSL / Example Shell	Title	Programming Notes	Deliverable			
3.41.	Safety	207966/primar y_02/T3.77	Summary of Sleep Disorder Adverse Events of Special Interest by System Organ Class and Preferred Term (Number of Subjects and Occurrences)		M12, M26, EOS			
3.42.	Safety	207966/primar y_02/T3.79	Summary of Weight Gain Adverse Events of Special Interest by System Organ Class and Preferred Term (Number of Subjects and Occurrences)		M12, M26, EOS			
3.43.	Safety	207966/primar y_02/T3.80	Summary of Rhabdomyolysis Adverse Events of Special Interest by System Organ Class and Preferred Term (Number of Subjects and Occurrences)		M12, M26, EOS			
3.44.	Safety	207966/primar y_02/T3.81	Summary of Pancreatitis Adverse Events of Special Interest by System Organ Class and Preferred Term (Number of Subjects and Occurrences)		M12, M26, EOS			
3.45.	Safety	207966/primar y_02/T3.82	Summary of Impact on Creatinine Adverse Events of Special Interest by System Organ Class and Preferred Term (Number of Subjects and Occurrences)		M12, M26, EOS			
3.46.	Safety	207966/primar y_02/T3.83	Summary of Safety in Pregnancy Adverse Events of Special Interest by System Organ Class and Preferred Term (Number of Subjects and Occurrences)		M12, M26, EOS			
3.47.	Safety	207966/primar y_02/T3.6	Summary of All Adverse Events by System Organ Class and Maximum Toxicity		HL, M12, M26, EOS			
3.48.	Safety	207966/primar y_02/T3.13	Summary of All Drug-related Adverse Events by System Organ Class and Maximum Toxicity		HL, M12, M26, EOS			

Safety:	Safety: Tables							

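### The Impact on Creatinine AESI list contains no creatinine, creatinine clearance or GFR result term, so Table 3.45 cannot report the effect it is named for

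*SAP*

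**What the plan says.** SAP Section 8.3, Table 4, lists Impact on Creatinine as an AESI with CAB+RPV as the drugs of interest. The reason given is "Regulatory Interest, Therapeutic Area, More prevalent in HIV population". The same section plans a summary by system organ class and preferred term for each AESI. For this one it is Table 3.45 (SAP Section 12.12.7): "Summary of Impact on Creatinine Adverse Events of Special Interest by System Organ Class and Preferred Term". That table uses the Safety population and, unlike the injection-site displays, is not limited to the Q2M arm.

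Appendix 10, item 17, states the concept as "Medical concept of worsening renal function/renal failure in the context of impact on creatinine". It then fixes the term set: "Only narrow terms from SMQ 'Acute renal failure' plus all PTs from HLT 'Renal failure and impairment', under SOC 'Renal and urinary disorders". Both term lists are printed in full.

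On AESIs in general, Appendix 10 says: "The adverse events of special interest are identified based on MedDRA coded values and/or AE data available in the study database". It also allows events to be added after review of accrued AE data before database freeze, and Section 8.3 allows the list of AESIs to change by the time of reporting. Neither clause requires a change or names a creatinine term.

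**The concern.** The AESI is named for a laboratory marker, and its stated concept mentions that marker. Its terms, however, are diagnoses, signs and procedures from renal failure groupings. Laboratory findings can be adverse events in this trial. Protocol Section 8.4.2 has investigators record clinically relevant laboratory changes in the AE section of the CRF, and Section 12.4.1 treats an abnormal laboratory result judged clinically significant as an AE. Section 8.7.7 directs attention to creatinine in particular, with a rule for "Participants who experience an increase in serum creatinine from Baseline of 45 micromoles/liter". A creatinine rise reported as an AE is therefore foreseeable.

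If such an event is coded to the laboratory result and not to a renal diagnosis, it falls outside item 17. Someone who goes straight to Table 3.45 for creatinine would find few or no participants and could conclude that there was no effect. The table's definition cannot support that conclusion.

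**Working it through.** No sample-size or power figure is involved. The check is a count of the printed terms and a comparison with neighbouring AESI lists.

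**Step 1: size of the list (SAP Appendix 10, item 17).**
- Rows under the SMQ: 19.
- Rows under the HLT: 27.
- Codes in both parts: 10 (acute kidney injury, anuria, foetal renal impairment, neonatal anuria, oliguria, prerenal failure, renal failure, renal failure neonatal, renal impairment, renal impairment neonatal).
- Distinct terms = 19 + 27 − 10 = 36.

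**Step 2: search for result terms.** The term names were searched for fragments of creatinine, glomerular, GFR, filtration, clearance, increased, decreased, blood and urine. The only hits are continuous haemodiafiltration and haemofiltration, which are procedures. Creatinine, creatinine clearance or GFR result terms: 0 of 36.

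**Step 3: effect on Table 3.45.** Let k be the number of participants whose only relevant event is coded to a creatinine or GFR result term. Under item 17 as written, these k participants contribute 0 to Table 3.45. The documents give no value for k. For scale, with the planned total of about 100 participants, each one is 1/100 = 1 percentage point of the whole study population. The split by arm is not fixed, because participants choose their regimen.

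**Step 4: where the same information does appear (SAP Section 12.12).**

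| Information | Display | Creatinine result included? |
|---|---|---|
| All AEs by SOC and preferred term | Table 3.01 | Yes, if reported as an AE |
| Chemistry change from baseline | Table 3.09 | Yes, measured values |
| Maximum emergent chemistry toxicity | Table 3.49 | Yes, graded values |
| All AEs, listed | Listing 13 | Yes, if reported as an AE |
| Impact on Creatinine AESI | Table 3.45 | No, unless coded to a listed renal term |

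**Step 5: is leaving out result terms a rule of the appendix?** It is not uniform.
- Result terms are present in Weight Gain (item 14), which draws in part on "HLT 'Physical examination procedures and organ system status', under SOC 'Investigations" and includes increased weight. They are also present in Rhabdomyolysis (item 15, increased blood myoglobin) and QT prolongation (item 4, which adds an ECG term from Investigations to its SMQ).
- The main laboratory marker is absent from the hepatic list (item 1: no ALT, AST or bilirubin term), Pancreatitis (item 16: no lipase or amylase term) and Rhabdomyolysis (item 15: no creatine phosphokinase term).

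So the appendix often leaves out the main marker. The difference in item 17 is that the AESI carries the marker's name.

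**The case against.** The best defence is that item 17 matches its stated concept, which is worsening renal function or renal failure. On that view the heading is loose and the term set is a deliberate choice of scope, in line with the hepatic, pancreatitis and rhabdomyolysis lists. This explains those three lists, which are named for conditions. It does not explain an AESI and a table title that name the marker itself.

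Several further points stand and limit what can be claimed:
- A reader might infer that investigator-reported creatinine events disappear from the report. They do not, because Table 3.01 shows every AE by preferred term.
- A reader might infer that the list captures only frank renal failure, or that nobody with a creatinine rise could be counted. The list includes renal impairment, renal injury, azotaemia and oliguria. Protocol Section 12.4.4 also prefers a diagnosis to individual signs where possible, so a rise recorded as renal impairment is counted.
- A reader might treat DTG as the main reason, since Protocol Section 2.3.1 notes that "Mild elevations of creatinine have been observed with DTG". That argument is secondary. The AESI is set for CAB+RPV, and the protocol describes the DTG effect as likely benign and without significant effect on GFR.

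The permission to extend the list means the gap could be closed before freeze. It is optional, though, and it relies on a blinded review of AE data in a study that Protocol Section 6.3 describes as open-label. Naming foreseeable terms in advance is firmer than adding them once events have accrued.

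**Conclusion.** The point holds as a defect in an AESI definition. None of the 36 distinct terms is a creatinine, creatinine clearance or GFR result, so a participant whose only event is coded to such a result is not counted in Table 3.45. This rests on two assumptions: that the event is coded to the result and not to a listed renal diagnosis, and that the discretionary extension is not used.

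The consequence is limited to interpretation. The table cannot report the effect in its title, and a low count could be misread. It would be tempting to state how many participants would be missed, but the documents give neither a rate of creatinine AEs nor any indication of how they would be coded, so no number is supported. No endpoint, analysis population or efficacy conclusion is affected, and the study's analyses are descriptive.

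**What to change.** In SAP Appendix 10, item 17, add the Investigations preferred terms for increased blood creatinine, decreased creatinine clearance and decreased GFR. The documents do not give the exact names and codes, so take them from the MedDRA version in use at reporting. In Table 3.45, show these terms as a block separate from the renal failure and impairment terms, so that the counts for the existing 36 terms stay unchanged and visible.

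The cost is a wording change and a small edit to the AESI look-up, with no new data. The overall AESI count may rise slightly and may include benign creatinine rises in the DTG + RPV arm. The separate block keeps those distinct from renal injury.
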